#### 5.1.3 Concomitant medication date imputation

Impute concomitant medication (CM) end date:

- 1. If CM end day is missing and CM month/year are non-missing then impute CM day as the minimum of treatment end date and the last day of the month.
- 2. If CM end day/month are missing and CM year is non-missing then impute CM day as the minimum of treatment end date and the end of the year (31DECYYYY).
- 3. If imputed CM end date is less than the CM start date, use the CM start date as the imputed CM end date.

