#### 2.4.2 Prior, concomitant and post therapies

Medications will be identified using the Novartis Drug and Therapy Dictionary (NovDTD) including Anatomical Therapeutic Chemical (ATC) code. Prior and concomitant treatments will be summarized in separate tables by treatment group for the SAF. Concomitant treatments will be displayed by study period as appropriate.

Medications will be presented in alphabetical order, by ATC codes and grouped by anatomical main group (the 1st level of the ATC codes). Tables will show the overall number and percentage of participants receiving at least one treatment of a particular ATC code and at least one treatment in a particular anatomical main group.

Prior medications are defined as treatments taken and stopped prior to first dose of study treatment. Any medication given at least once between the day of first dose of randomized study treatment and within 84 days after last dose will be a concomitant medication, including those which were started before first dose of study treatment and continued into the period where study treatment is administered.

Prior or concomitant medication will be identified by comparing recorded or imputed start and end dates of medication taken to the reference start date. See Section 5.1.3 for details.

Significant prior and concomitant non-drug therapies and procedures will be summarized by primary system organ class and MedDRA preferred term.

Prior non-drug therapies and procedures are defined as non-drug therapies and procedures done prior to first dose of study treatment. Any non-drug therapies and procedures done between the day of first dose of study treatment and within 84 days after last dose will be defined as concomitant non-drug therapies and procedures, including those which were started before first dose of study treatment and continued into the period where study treatment is administered.

The number and percentage of participants receiving prior and concomitant RCT therapy will be presented by randomized treatment group.

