## 5.1.2 AE date imputation

Impute AE end date:

- 1. If the AE end date 'month' is missing, the imputed end date should be set to the earliest of the (min (last visit date, last dose date + 84 days), 31DECYYYY, date of death).
- 2. If the AE end date 'day' is missing, the imputed end date should be set to the earliest of the (min (last visit date, last dose date + 84 days), last day of the month, date of death).
- 3. If AE 'year' is missing or AE is ongoing, the end date will not be imputed.

Impute AE start date:

Before imputing AE start date, find the AE start reference date as below

- If the (imputed) AE end date is complete and the (imputed) AE end date < treatment start date then AE start reference date = min (informed consent date, earliest visit date).
- Else AE start reference date = treatment start date
- 1. If the AE start date 'year' value is missing, the date uncertainty is too high to impute a rational date. Therefore, if the AE year value is missing, the imputed AE start date is set to NULL.
- 2. If the AE start date 'year' value is less than the treatment start date year value, the AE started before treatment. Therefore:
  - a. If AE 'month' is missing, the imputed AE start date is set to the mid-year point (01JulYYYY).
  - b. Else if AE 'month' is not missing, the imputed AE start date is set to the midmonth point (15MONYYYY).
- 3. If the AE start date year value is greater than the treatment start date year value, the AE started after treatment. Therefore:
  - a. If the AE month is missing, the imputed AE start date is set to the year start point (01JanYYYY).
  - b. Else if the AE month is not missing, the imputed AE start date is set to the later of (month start point (01MONYYYY), AE start reference date + 1 day).

4. If the AE start date year value is equal to the treatment start date year value:

- a. And the AE month is missing the imputed AE start date is set to the AE reference start date + 1 day.
  - b. Else if the AE month is less than the treatment start month, the imputed AE start date is set to the mid-month point (15MONYYYY).
  - c. Else if the AE month is equal to the treatment start date month or greater than the treatment start date month, the imputed AE start date is set to the later of (month start point (01MONYYYY), AE start reference date + 1 day).

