#### Impute CM start date:

- 1. If the CM start date year value is missing, the imputed CM start date is set to one day prior to treatment start date.
- 2. If the CM start date year value is less than the treatment start date year value, the CM started before treatment. Therefore:
  - a. If the CM month is missing, the imputed CM start date is set to the mid-year point (01JulYYYY).
  - b. Else if the CM month is not missing, the imputed CM start date is set to the mid-month point (15MONYYYY).
- 3. If the CM start date year value is greater than the treatment start date year value, the CM started after treatment. Therefore:
  - a. If the CM month is missing, the imputed CM start date is set to the year start point (01JanYYYY).
  - b. Else if the CM month is not missing, the imputed CM start date is set to the month start point (01MONYYYY).
- 4. If the CM start date year value is equal to the treatment start date year value:
  - a. And the CM month is missing or the CM month is equal to the treatment start date month, then the imputed CM start date is set to one day prior treatment start date.
  - b. Else if the CM month is less than the treatment start date month, the imputed CM start date is set to the mid-month point (15MONYYYY).
  - c. Else if the CM month is greater than the treatment start date month, the imputed CM start date is set to the month start point (01MONYYYY).

If complete (imputed) CM end date is available and the imputed CM start date is greater than the (imputed) CM end date, then imputed CM start date should be set to the (imputed) CM end date.

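### An undefined treatment-end cap on partial medication end dates (SAP 5.1.3) can override a recorded later month and, if the start is partial too, date a follow-up drug into Study period 1

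*SAP*

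**What the plan says.** SAP 5.1.3 gives three rules for a partial concomitant-medication (CM) end date.

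- Rule 1 (day missing): "impute CM day as the minimum of treatment end date and the last day of the month".
- Rule 2 (day and month missing): the same construction, with 31 December of the recorded year in place of the month end.
- Rule 3: "If imputed CM end date is less than the CM start date, use the CM start date as the imputed CM end date".

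For partial start dates in the year of first dose, rule 4c reads: "Else if the CM month is greater than the treatment start date month, the imputed CM start date is set to the month start point". The section closes with an override for an imputed start later than the end: "then imputed CM start date should be set to the (imputed) CM end date". Section 5.1.3.2 applies all of this to post therapies as well.

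SAP 2.4.2 sets the window and the display. Medication given from first dose to "within 84 days after last dose will be a concomitant medication", and "Concomitant treatments will be displayed by study period as appropriate". Dosing stops at Week 12, Study period 1 runs from baseline to Week 16, and follow-up runs to Week 24 (SAP 1.1).

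The adverse-event rule in SAP 5.1.2 uses a different cap when the end day is missing: the earliest of "min (last visit date, last dose date + 84 days), last day of the month, date of death".

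The SAP does not define *treatment end date*, and 5.1.3 does not say whether start or end dates are imputed first.

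**The concern.** An imputation rule should fill in what is missing and leave what was recorded alone. Rules 1 and 2 make no exception for a recorded month or year later than the cap. Medication is followed for 84 days after last dose, so such records are to be expected. The cross-reference from post therapies shows the oddity: those drugs would have their end dates capped at treatment end.

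What is at stake is the display of medication by study period, where use of non-study drugs before and after Week 16 would be read. After early termination the SAP drops sensitivity and supplementary analyses (2.5.4, 2.6.5). The protocol's supplementary estimand for rescue medication (Protocol 9.3.7) therefore has no counterpart, and the medication tables are one of the few remaining views of such use.

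**Working it through.** The plan gives no figure for this rule, so there is none to reproduce. The check applies the rules literally to example records.

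**Inputs.** First dose is assumed to be 10 Jan 2024, and Day n = first dose + (n − 1). From the SAP visit windows and Protocol Table 1-2:

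- Week 12 = Day 85 = 3 Apr
- Week 16 = Day 113 = 1 May
- Week 24 = Day 169 = 26 Jun

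Last dose + 84 days = Day 85 + 84 = Day 169.

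**Formulas.** Imputed end = min(cap, last day of recorded month). If end < a complete start, end = start (rule 3). If an imputed start > end, start = end (final override). The end is imputed first.

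**Records.** All three have a recorded end of June 2024 with the day missing, so the month end is 30 Jun.

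- A: complete start 1 Mar (Day 52), on treatment.
- B: complete start 20 May (Day 132), in follow-up.
- C: partial start June, imputed to 1 Jun (Day 144) by rule 4c, in follow-up.

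| Cap read as | A | B | C |
|---|---|---|---|
| Last dose, Day 85 | Day 52 to 85 | Day 132 to 132 | Day 85 to 85 |
| Week 16 visit, Day 113 | Day 52 to 113 | Day 132 to 132 | Day 113 to 113 |
| Last dose + 84, Day 169 | Day 52 to 169 | Day 132 to 169 | Day 144 to 169 |

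Under the first two readings the recorded June end is lost in every record, with three different consequences:

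- A loses its follow-up use but was already in Study period 1.
- B: the cap gives 3 Apr or 1 May, which is before 20 May, so rule 3 sets the end to 20 May. The drug stays in follow-up as one day.
- C: the end becomes 3 Apr or 1 May, and the start of 1 Jun is pulled back to it. The start moves by 144 − 85 = 59 days or 144 − 113 = 31 days, into Study period 1 (on its last day under the Week 16 reading).

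**Order.** If the start of C is imputed first, 1 Jun stands, the capped end falls before it, and rule 3 sets the end to 1 Jun. The drug then stays in follow-up with its month kept, as one day. The override's reference to an imputed end date points to end-first, but the order is not stated.

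**Rule 2.** Suppose last dose is 15 Nov 2023 and Week 24 is 84 days later, on 7 Feb 2024. A drug recorded as ending in 2024 gets min(15 Nov 2023, 31 Dec 2024) = 15 Nov 2023, so the recorded year is lost.

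**Is the adverse-event cap enough?** Participants who stop treatment early should still attend to Week 24 (Protocol 1.3, 7.1). Take a last dose at Week 4 (Day 29 = 7 Feb) and a last visit on Day 169. Last dose + 84 = Day 113 = 1 May. A drug recorded as ending in June gets min(26 Jun, 1 May, 30 Jun) = 1 May, and June is overridden again. Capping at the last visit gives min(26 Jun, 30 Jun) = 26 Jun, and June is kept.

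**Size.** The cap lies 169 − 85 = 84 days (12 weeks) or 169 − 113 = 56 days (8 weeks) before Week 24. With 21 randomized at termination (SAP 1), an arm has about 21/2 = 10.5 participants, so one participant is 1/10.5 = 9.5 percentage points.

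**The case against.** The strongest reply is that *treatment end date* is undefined and the SAP elsewhere runs the on-treatment period to last dose + 84 days (2.1.1.4, 2.7). On that reading nothing moves for a completer, as the last row of the table shows. This stands in part: the text does not exclude that reading. But 5.1.2, one section earlier, writes the 84-day limit out in full when it is meant, and 5.1.3 uses treatment start date throughout for first dose, so last dose is the natural counterpart. The 84-day reading also still fails for early discontinuers.

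Second, the shift in record C needs a partial start as well as a partial end, and the end-first order. That stands. A reader might infer that the rule moves follow-up medication into the treatment period in general. The documents do not support this: rule 3 keeps a drug with a complete follow-up start in follow-up, and a drug begun on treatment is truncated, not moved.

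Third, the tables at risk are limited. SAP 2.4.2 plans by-period display only where appropriate, and counts participants with at least one treatment per ATC code. The one-day collapse of record B changes no such count, and no summary of CM duration is planned there. A reader might also infer that NSAID dose increases would be misplaced in these tables. ATC counts do not show dose increases. Those are recorded as protocol deviations (Protocol 4.3.1, 6.8.3), which SAP 2.3.1 tabulates.

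**Conclusion.** The concern holds in a limited form. As written, rules 1 and 2 can replace a recorded month or year with an earlier one, provided that *treatment end date* means last dose or the Week 16 visit. A follow-up drug enters Study period 1 only if its start date is also partial and the end is imputed first.

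The effect is confined to CM dates and the by-period CM display. No drug crosses between prior and concomitant, because the cap never precedes first dose. No efficacy result is touched: those analyses are descriptive and do not use CM dates. One might also infer that the adverse-event cap is the right substitute; the Week 4 example shows it is not sufficient on its own.

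The documents do not say how many partial dates there are, so the effect may be zero. The figure of about 10 percentage points for one participant rests on the 21 randomized at termination. Participants already screened could continue, so the final arms may be larger and the figure smaller. This is a minor point, worth correcting because the rule can give wrong dates and the change is nearly free.

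**What to change.** In SAP 5.1.3:

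1. In rules 1 and 2, replace treatment end date by the participant's last visit (end of study) date.
2. State that an imputed date may never fall outside the recorded month or year, and that this takes precedence over the cap and the final start-date override. It covers a drug reported after the last visit, for example at the safety follow-up call in Protocol 4.7.
3. State the order in which start and end dates are imputed, and where rule 3 and the final override apply in it.

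The cost is a few lines of SAP text and the matching change to the date derivation; no new data are needed. One side effect should be noted: start-date rule 4a sets a start in the month of first dose to the day before dosing. If first dose falls on the first of a month, item 2 would move that start to the first, and the drug would still be concomitant if it continued.

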#### Impute CM start date:

- 1. If the CM start date year value is missing, the imputed CM start date is set to one day prior to treatment start date.
- 2. If the CM start date year value is less than the treatment start date year value, the CM started before treatment. Therefore:
  - a. If the CM month is missing, the imputed CM start date is set to the mid-year point (01JulYYYY).
  - b. Else if the CM month is not missing, the imputed CM start date is set to the mid-month point (15MONYYYY).
- 3. If the CM start date year value is greater than the treatment start date year value, the CM started after treatment. Therefore:
  - a. If the CM month is missing, the imputed CM start date is set to the year start point (01JanYYYY).
  - b. Else if the CM month is not missing, the imputed CM start date is set to the month start point (01MONYYYY).
- 4. If the CM start date year value is equal to the treatment start date year value:
  - a. And the CM month is missing or the CM month is equal to the treatment start date month, then the imputed CM start date is set to one day prior treatment start date.
  - b. Else if the CM month is less than the treatment start date month, the imputed CM start date is set to the mid-month point (15MONYYYY).
  - c. Else if the CM month is greater than the treatment start date month, the imputed CM start date is set to the month start point (01MONYYYY).

If complete (imputed) CM end date is available and the imputed CM start date is greater than the (imputed) CM end date, then imputed CM start date should be set to the (imputed) CM end date.

#### 5.1.3.1 Prior therapies date imputation

See Section 5.1.3.

#### 5.1.3.2 Post therapies date imputation

See Section 5.1.3.

## 5.1.4 First diagnosis date imputation

- 1. If the first diagnosis day/ month are missing and the year is non-missing:
  - a. If the year part of the first diagnosis date is equal to the year part of the inform consent date, then the imputed first diagnosis date is set to the year start point (01JanYYYY).
  - b. Otherwise the imputed first diagnosis date is set to the mid-year point (01JulYYYY).
- 2. If the first diagnosis day is missing and the month/year are non-missing:
  - a. If the month and year part of the first diagnosis date is equal to the month and year part of the inform consent date, then the imputed first diagnosis date is set to the month start point (01MONYYYY).
  - b. Otherwise the imputed first diagnosis date is set to the mid-month point (15MONYYYY).

## 5.1.5 Other imputations

#### 5.1.5.1 Laboratory data

For laboratory test values below Lower Level of Quantification (LLQ) or above Upper Level of Quantification (ULQ) will be imputed as LLQ or ULQ value, respectively. The numerical part of the reported result will be treated as the actual LLQ or ULQ. These laboratory values will be displayed in listings using the standard unit with the reported sign ("<" or ">").

#### 5.2 AEs coding/grading

Adverse events will also be coded according to MedDRA dictionary, using a narrow search. The MedDRA version used for reporting the adverse events will be described in a footnote. Safety topics of interest, such as risks defined in the Safety Profiling Plan, topics of interest regarding signal detection or routine analysis are defined in the Program Case Retrieval Sheet.

#### 5.3 Laboratory parameters derivations

See Table 2-4 and Table 2-5.

#### 5.4 Statistical models

#### 5.4.1 Summary statistics for binary and categorical data

Summary statistics for discrete variables will be presented in contingency tables and will include count and frequency in each category. If applicable, confidence intervals will be derived as well based on the score method including continuity correction (Newcombe 1998):

With z as  $(1-\alpha/2)$ -quantile of the standard normal distribution (SAS:  $z = probit(1-\alpha/2)$ , n as total number of participants (i.e., number of participants in the denominator), p as estimated crude incidence (number of participants with event / n) and q = 1-p

Then the lower limit is

$$L = 100 \times \max \left(0, \frac{2np + z^2 - 1 - z\sqrt{z^2 - 2 - \frac{1}{n} + 4p(nq + 1)}}{2(n + z^2)}\right)$$

and the upper limit is

$$U = 100 \times \min \left( 1, \frac{2np + z^2 + 1 + z\sqrt{z^2 + 2 - \frac{1}{n} + 4p(nq - 1)}}{2(n + z^2)} \right).$$

In addition, if L > p then L = p and if U < p then U = p.

For binary response variables the placebo-adjusted response rates including 95% confidence interval will be derived.

SAS code for risk difference:

proc freq data=;

tables response\* treatment / riskdiff;

run

Note the response value should be sorted with '1' ahead of '0'.

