## 2.6.2 Statistical hypothesis, model, and method of analysis

The secondary objectives will be analyzed in a purely descriptive manner. Categorical variables will be presented in frequency tables. PROMIS change from baseline over time will be presented by treatment group using a summary table. No testing strategy will be applied.

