#### 2.7.1 Adverse events (AEs)

All information obtained on adverse events will be displayed by treatment group and participant.

The number (and percentage) of participants with treatment emergent adverse events will be summarized in the following ways:

- by treatment, primary system organ class and preferred term.
- by treatment, primary system organ class, preferred term and maximum severity.

Confidence intervals for the crude rate will be derived as described in Section 5.4.

Treatment emergent adverse events are defined as events started on or after the first dose of study medication or events present prior to the first dose of study medication but increased in severity on or after dosing based on preferred term and within last dose + 84 days (inclusive).

A participant with multiple adverse events within a primary system organ class is only counted once towards the total of the primary system organ class.

Separate summaries will be provided for study treatment related adverse events, death, serious adverse event, other significant adverse events leading to discontinuation and adverse events leading to dose adjustment or interruption.

Adverse events reported will be presented in descending frequency according to its incidence in the AIN457 300 mg group starting from the most common event. AEs will be summarized by presenting the number and percentage of participants having any AE, having an AE in each primary system organ class and having each individual AE (preferred term).

Summaries will also be presented for AEs by severity and for study treatment related AEs. If a particular AE 'severity' is missing, this variable will be listed as missing and treated as missing in summaries. If a participant reported more than one adverse event with the same preferred term, the adverse event with the greatest severity will be presented. If a participant reported more than one adverse event within the same primary system organ class, the participant will be counted only once with the greatest severity at the system organ class level, where applicable. Of note, AEs by severity will be provided by SOC in the study report and AEs by severity and PTs may be provided if required at ad-hoc basis.

The MedDRA version (version 27.0 or above) used for reporting the study will be described in a footnote.

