#### 5.4.2 Crude incidence and related risk estimates

## 5.4.2.1 Crude incidence and $100*(1-\alpha)\%$ confidence interval

For *n* participants, each at risk to experience a certain event with probability  $\pi$ , the crude incidence is estimated as p=x/n, where *x* is the number of participants with the event.

Absolute and relative frequencies will be displayed as well as 95% confidence interval for the relative frequency based on the score method including continuity correction (Newcombe 1998).

With z as  $(1-\alpha/2)$ -quantile of the standard normal distribution (SAS:  $z = PROBIT(1-\alpha/2)$ , n as total number of participants (i.e., number of participants in the denominator), and p as estimated crude incidence (number of participants with event / n) it is q=1-p.

Then the lower limit is

$$L = \max\left(0, \frac{2np + z^2 - 1 - z\sqrt{z^2 - 2 - \frac{1}{n} + 4p(nq + 1)}}{2(n + z^2)}\right)$$

and the upper limit is

$$U = \min\left(1, \frac{2np + z^2 + 1 + z\sqrt{z^2 + 2 - \frac{1}{n} + 4p(nq - 1)}}{2(n + z^2)}\right).$$

In addition, if L > p then L = p and if U < p then U = p.

If appropriate, an exact  $100*(1-\alpha)\%$  confidence interval (Clopper-Pearson, 1934) will be obtained by using the SAS procedure PROC FREQ with the EXACT BINOMIAL statement. However, the confidence interval derived via the score method including continuity correction will be the default in safety analyses.

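### SAP 5.4.1 puts the score confidence limits on the percent scale but truncates them against a proportion, so any interval programmed from it has a wrong lower limit whenever there is at least one event

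*SAP*

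**What the plan says.** SAP 5.4.1 (binary and categorical summaries) offers, where applicable, a score interval with continuity correction. Its symbols include "p as estimated crude incidence (number of participants with event / n) and q = 1-p", so p runs from 0 to 1. The printed limits are L = 100 × max(0, …) and U = 100 × min(1, …), which run from 0 to 100. The section then adds "In addition, if L > p then L = p and if U < p then U = p", with no factor 100 on p.

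The same section goes on: "For binary response variables the placebo-adjusted response rates including 95% confidence interval will be derived". The SAS code given for that is a PROC FREQ risk difference.

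SAP 5.4.2.1 repeats the two formulas and the truncation sentence without the factor 100. There "the crude incidence is estimated as p=x/n", and "Absolute and relative frequencies will be displayed as well as 95% confidence interval for the relative frequency based on the score method" with continuity correction.

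Two sections bear on which version gets used. For adverse events, SAP 2.7.1 says "Confidence intervals for the crude rate will be derived as described in Section 5.4" and does not choose between 5.4.1 and 5.4.2.1. For the responder endpoints, SAP 2.6.2 says only "Categorical variables will be presented in frequency tables".

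**The concern.** The truncation has a real job. With this interval the raw lower limit at zero events lies above 0, and the raw upper limit at full response lies below 100%. The rule pulls each back to the observed rate. That works only if L, U and p share a scale. In 5.4.1 they do not, so the rule acts where it should not (the lower limit for every non-zero count) and fails where it is needed (the upper limit at full response).

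At stake is any single-proportion interval programmed from 5.4.1. This could include intervals added to the descriptive responder tables (WORC-PSD40 at Weeks 16 and 24, WORC-TOT50 at Week 16). It could also include crude adverse-event rates, if a programmer takes the first formula found under Section 5.4.

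**Working it through.** **Inputs.** The formulas, the definition of p and the truncation rule come from SAP 5.4.1; the comparison version comes from 5.4.2.1. The level is 95% two-sided, so z = 1.96 and z² = 3.8415. SAP Section 1 reports 21 randomized at termination, and n = 10 per arm is assumed from the 1:1 ratio. The SAP states no numerical interval, so there is no printed figure to reproduce.

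**Step 1. The formulas before truncation are sound.** Before the factor 100:

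- lower = [2np + z² − 1 − z√(z² − 2 − 1/n + 4p(nq + 1))] / [2(n + z²)]
- upper = [2np + z² + 1 + z√(z² + 2 − 1/n + 4p(nq − 1))] / [2(n + z²)]

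For 6/10 (p = 0.6, q = 0.4) the denominator is 2 × 13.8415 = 27.683.

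- Lower: (12 + 3.8415 − 1 − 1.96 × √13.7415) / 27.683 = (14.8415 − 7.2655) / 27.683 = 0.2737
- Upper: (12 + 3.8415 + 1 + 1.96 × √12.9415) / 27.683 = (16.8415 + 7.0508) / 27.683 = 0.8631

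Direct inversion of |p − P| − 1/(2n) = z√(P(1 − P)/n) gives the same limits, 27.367% and 86.307%. The two methods agreed to three decimals in all eight cases tried.

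**Step 2. The rule applied as printed in 5.4.1.** For 6/10, L = 27.37 and p = 0.6. Since 27.37 > 0.6, L is set to 0.6. U = 86.31 is not below 0.6, so it stays.

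For 10/10, the raw limits are 65.55 and 99.08, and p = 1. L is set to 1. U should be raised to 100, but 99.08 is not below 1, so nothing happens.

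For 0/10, the raw lower limit is 0.92 and p = 0. L is set to 0, which is right because zero is the same on both scales.

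**Step 3. The rule on one scale, as in 5.4.2.1, then multiplied by 100.**

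| Events/n | 5.4.1 as printed | One scale (%) |
|---|---|---|
| 0/10 | 0 to 34.45 | 0 to 34.45 |
| 1/10 | 0.10 to 45.88 | 0.52 to 45.88 |
| 5/10 | 0.50 to 79.86 | 20.14 to 79.86 |
| 6/10 | 0.60 to 86.31 | 27.37 to 86.31 |
| 10/10 | 1.00 to 99.08 | 65.55 to 100 |
| 70/117 (planned arm size, illustration only) | 0.60 to 68.66 | 50.34 to 68.66 |

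**Step 4. How general it is.** Over all n from 1 to 500 with at least one event (125,250 combinations), the printed rule sets L = p every time, because the percent lower limit is never less than 5.2 times p. The result is below 1 when 0 < x < n and exactly 1 when x = n. The upper limit differs from the correct one only at x = n (500 cases). At x = 0 both limits are correct.

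**The case against.** The strongest reply is that little in the amended plan calls for this interval. A reader might infer that the error bars of the retained responder endpoints will all be wrong. The documents do not support that:

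- Section 2.6.2 asks for frequency tables, with no per-arm interval or figure.
- The one-sample interval in 5.4.1 is conditional.
- The one interval that 5.4.1 firmly assigns to binary responses is the placebo-adjusted rate. It comes from the risk-difference code and does not use L or U.

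For safety, the terms crude rate (2.7.1) and crude incidence (liver events, 2.7.3) match the title of 5.4.2. Section 5.4.2.1 is consistent and calls its score interval the safety default. The intended method is clear, and an interval of 0.6 to 86.3 around 60% would probably be noticed when the dry-run outputs are reviewed.

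All of this stands, and it limits the consequence. It does not make the printed rule right: no reading of the 5.4.1 definitions puts L, U and p on one scale. Nor does it remove the ambiguity in 2.7.1, which cites Section 5.4 as a whole when that section holds one valid and one invalid version.

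**Conclusion.** Minor, but wrong as written. Followed literally, 5.4.1 gives a lower limit equal to p, hence at most 1 on the percent scale, for every count of one or more, and an upper limit that falls short of 100 at full response. At an assumed 10 per arm, the lower limit for 6 responders is about 27 percentage points too low (27.4 against 0.6), and for 10 responders about 65 points too low (65.6 against 1.0).

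The error reaches only intervals actually programmed from 5.4.1: optional ones for the responder tables, and possibly crude adverse-event rates. Intervals from 5.4.2.1 and the risk difference are unaffected. The amended analysis is descriptive, so no test, power figure or decision depends on the rule.

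The arm size is an assumption. Patients screened by 7 May 2024 could continue, so the final number is not fixed at 21. The direction of the error does not depend on n.

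**What to change.** Any one of these repairs 5.4.1:

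- compare and replace with 100p: if L > 100p then L = 100p, and if U < 100p then U = 100p;
- drop the factor 100, truncate on the proportion scale, and multiply by 100 for display;
- delete the 5.4.1 formulas and refer to 5.4.2.1.

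The third is cleanest, because it leaves one definition of the interval. In addition, change the cross-reference in 2.7.1 from Section 5.4 to Section 5.4.2.1.

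The cost is a line or two of SAP wording and, if the 5.4.1 rule has already been programmed, one line of code. Data collection, analysis sets and endpoints do not change.
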